7.1 Analysis Populations

7.1.1 Participant Analysis Populations

7.1.1.1 Enrolled Population

The enrolled set will consist of all participants who sign the ICF.

7.1.1.2 Full Analysis Population

The full analysis population will consist of all participants who were randomised to treatment.

All analyses using the full analysis population will group participants according to randomised treatment.

7.1.1.3 Safety Population

The safety population will consist of all participants who received any study drug.

All analyses using the safety population will group participants according to actual treatment received. If participants received multiple treatment during the study, they will be assigned to treatment group in the following manner:

- If participant received both active EDP and placebo treatments, they will be assigned to the active treatment group.
- If participant received 2 or more different active dose levels, they will be assigned to the highest dose they received.

7.1.2 Defined Data Point Sets

Efficacy data point sets 1-6 were designed to replicate the corresponding primary endpoint estimands intercurrent event strategies:

- EDPS1 corresponds to primary estimand 1.
- EDPS2 corresponds to supplementary estimand 1.
- EDPS3 corresponds to supplementary estimand 2.
- EDPS4 corresponds to supplementary estimand 3.
- EDPS5 corresponds to supplementary estimand 4.
- EDPS6 corresponds to supplementary estimand 5.

The following definitions and computational methods applied to the data point sets:

* TCS/TCI rescue therapy – is the rescue therapy when topical corticosteroid or calcineurin inhibitors medication was prescribed. Rescue therapy is reported in both the CRF and patient diary. For the analysis purposes rescue therapy recorded on CRF page will be used.

Multiple periods with rescue therapy are allowed during the study. All periods with rescue therapy are considered in EDPS definitions.

** Study withdrawal reasons related to study medication are lack of efficacy, treatment failure, adverse event (if related). Also, withdrawal of consent may be considered related to study medication based on the clarification text provided, that will be assessed by the Evelo team and provided in a separate spreadsheet. Type 2 prohibited medication will be considered as treatment withdrawal due to related reason at the date of medication start. Non-related reasons are all other reasons.

¹Last off-rescue observation is defined as the last off-rescue observation in the period before the corresponding intercurrent event plus early termination visit in case of early study discontinuation (off-rescue is defined as data collected at least 28 days after use of rescue medication or type 1 prohibited medication).

Categorization of all concomitant medications prescribed during the study will be done by Evelo clinician in order to identify TCS/TCI rescue therapy, antimicrobial rescue therapy and prohibited medications of type 1 and 2.

7.1.2.1 Efficacy Data Point Set 1 (EDPS1)

EDPS1 consists of all data collected at a scheduled timepoint that is at least 28 days after use of TCS/TCI rescue therapy* or type 1 prohibited medication and before use of type 2 prohibited medication. Data collected less than 28 days after such use or data missing due to withdrawal from the study for reasons considered related to study medication** or data collected after use of type 2 prohibited medications will be replaced as follows:

- Continuous endpoints: value will be imputed with the last off-rescue¹ observation in the period before the event plus early termination visit in case of early study discontinuation (off-rescue is defined as data collected at least 28 days after use of rescue medication or type 1 prohibited medication)
- Responder endpoints: value will be imputed as non-response.
- Count endpoints: N/A (no count endpoint will use this DPS).

Data missing for other reasons, including early withdrawal from the study due to reasons not considered related to study medication will not be replaced and will be considered as missing.

Example 1: if patient completed 16 weeks of study with rescue therapy during week 3 and then during week 10 then responder endpoints will be analysed as shown in table:

Week 0	Week 2	Week 4	Week 8	Week 12	Week 16
As collected	As collected	Imputed as non-responder because there was a rescue therapy within 28 days before Week 4 visit	As collected	Imputed as non-responder because there was a rescue therapy within 28 days before Week 12 visit	As collected

Example 2: if patient completed 16 weeks of study with rescue therapy from Day 25 to Day 31 then responder endpoints will be analysed as shown in table:

Week 0	Week 2	Week 4	Week 8	Week 12	Week 16
As collected	As collected	Imputed as non-responder because there was a rescue therapy within 28 days before Week 4 visit	Imputed as non-responder because there was a rescue therapy within 28 days before Week 4 visit	As collected	As collected

Example 3: if patient withdrew study early due to the lack of efficacy after 12 weeks of treatment with rescue therapy during week 3 (unscheduled rescue therapy visit was not done) and then during week 10 (unscheduled rescue therapy visit was done at Week 9 prior to the rescue therapy start) then continuous endpoints will be analysed as shown in table:

Week 0	Week 2	Week 4	Week 8	Week 12	Week 16
As collected	As collected	Imputed with Week 2 data because there was a rescue therapy within 28 days before Week 4 visit and the last off-rescue data is at Week 2 visit	As collected	Imputed with Week 9 data because there was a rescue therapy within 28 days before Week 12 visit and the last off-rescue data is at unscheduled Week 9 visit	Imputed with Week 9 data because visit is missing due to reasons considered related to study medication and the last off-rescue data is at unscheduled Week 9 visit

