1. INTRODUCTION

1.1. Atopic Dermatitis

Atopic dermatitis (AD), also known as (atopic) eczema, is a chronic, highly symptomatic relapsing inflammatory skin disease, affecting up to 30% of children and 10% of adults (Bieber, Atopic Dermatitis, 2010). While AD often begins in infancy or childhood, it may become chronic and persist into adulthood (Katoh, 2019). Depending on factors such as severity of skin lesions or body surface area coverage, the disease can be classified clinically as mild, moderate, or severe.

Patients with AD typically have highly symptomatic skin lesions that may present acutely with erythema, exudates, papulovesicles, scales and crusts, often symmetrically distributed on the body (Katoh, 2019). The disease typically follows a variable course with acute flares, often triggered by external factors, which cause a worsening of skin disease and symptoms. More chronic lesions are associated with thickened lichenified skin which may be accompanied by pigmentary changes and further excoriations (Bieber, Atopic Dermatitis, 2010). The primary symptom at both stages of disease is typically pruritus (itch). Such signs and symptoms are associated with a substantial patient burden that typically includes sleep disturbance, mood disturbance and mental health problems (Simpson, 2012), poor quality of life, and social functioning (Kiebert, 2002).

AD, like other atopic disease, is characterized by a T helper type 2 (Th2) cell-mediated inflammation, with up-regulation of Th2 cytokines including IL-4, IL-5, and IL-13 (Indra, 2013). In turn, this leads to increased IgE production by B-cells, which can trigger release of cytokines and chemical mediators such as histamine from mast cells and Langerhans cells. In addition, thymic stromal lymphoprotein is thought to be a critical cytokine in the triggering and maintenance of AD (Indra, 2013), and is associated with migration of Th2 cells into the skin lesion (Katoh, 2019). The resulting systemic inflammation drives the disease pathology and patient symptoms, with the resultant scratching of pruritic lesions further worsening the skin lesions and the skin barrier function, further driving the disease process. Therefore, targeting systemic inflammation improves disease signs and symptoms – for example systemic corticosteroids typically lead to rapid clinical improvements, but generally are not acceptable as a long-term treatment due to associated side-effects (Lee, 2016).

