7.9. Early Termination Visit

Participants who withdraw prematurely from the study should have an early termination visit using the Early Termination Visit schedule within 14 days of asking to withdraw consent or within 72 hours of starting any AD therapy if their withdrawal was due to treatment failure. The participant will also be asked to have a final telephone call 28 days (+3 days) after taking their last dose of IMP for safety assessments. The date of this telephone call will be considered the end of study date for these participants.

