9.4.1.1 Estimands

The population summary measure of interest will be the mean difference between treatment groups specified in [Section 9.4](#).

Where intercurrent event strategy is composite, for continuous endpoints value will be imputed with the last off-rescue observation.

Last off-rescue observation is defined as the last off-rescue observation in the period before the corresponding intercurrent event plus early termination visit in case of early study discontinuation (off-rescue is defined as data collected at least 28 days after use of rescue medication or type 1 prohibited medication).

Note, for PP-NRS and SD-NRS intercurrent event strategy should be applied for daily scores before the weekly scores are calculated.

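### For continuous endpoints, the EDPS1 carry-forward rule does not stop an Early Termination score taken on a type 2 medication from being carried to Week 16

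*SAP*

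**What the plan says.** SAP 7.1.2.1 admits to EDPS1 only data that precede any type 2 medication, and states that "data collected after use of type 2 prohibited medications will be replaced as follows". For continuous endpoints the replacement (the donor value) is the last off-rescue observation "in the period before the event plus early termination visit in case of early study discontinuation". SAP 7.1.2, 9.4.1.1 and 9.5.1 repeat the rule, and 9.4.1.1 ties it to the estimand: "Where intercurrent event strategy is composite, for continuous endpoints value will be imputed with the last off-rescue observation".

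Eligibility as a donor depends on one definition: "off-rescue is defined as data collected at least 28 days after use of rescue medication or type 1 prohibited medication". Type 2 medication is not named in it. The event date is fixed in SAP 7.1.2: "Type 2 prohibited medication will be considered as treatment withdrawal due to related reason at the date of medication start". EDPS2 (SAP 7.1.2.2) handles data after type 2 use in the same way as EDPS1.

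On the protocol side, section 5.4 defines treatment failure by the participant commencing phototherapy, an oral agent, a biological or certain topical therapy, and requires withdrawal. Section 7.9 asks for the ET visit "within 72 hours of starting any AD therapy if their withdrawal was due to treatment failure". Footnote a of Table 4-1 says the same and adds that this applies when possible.

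SAP 7.7 excludes the ET visit from summary and analysis tables. Its exceptions are baseline values, worst-case safety endpoints and rescue unscheduled visits, and it provides for carry-forward only from the last of these.

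**The concern.** The ET clause makes sense for someone who leaves for lack of efficacy or a related adverse event without starting another treatment: the ET visit is then the last observation that reflects the study regimen. For a type 2 user the same clause can point to a score taken after the new therapy began. The rule would then put back the kind of observation it is meant to remove.

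The definition is also uneven. A type 1 product such as a bleach bath disqualifies a donor value for 28 days. A systemic immunosuppressant or phototherapy disqualifies it for none, although SAP section 13 justifies the type 1 and type 2 split by the potential of prohibited medications to affect efficacy. Protocol 1.1 itself remarks that "systemic corticosteroids typically lead to rapid clinical improvements".

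At stake are the continuous scores collected at ET: EASI, BSA, vIGA*BSA, SCORAD, DLQI and POEM among the secondary endpoints, and SF-12, HADS, ADCT and change from screening in EASI among the exploratory ones. A treatment failure could be credited with another drug's effect at every visit after the event. If failures were commoner on placebo, the treatment difference would shrink.

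**Working it through.** The plan gives no figure for this point. Its one worked case of early withdrawal, Example 3 in SAP 7.1.2.1, can be used to check a reading of the rule.

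**Inputs.** Visit days 1, 15, 29, 57, 85 and 113 (Protocol Table 4-1); the donor rule (SAP 7.1.2.1); the 28-day off-rescue condition (SAP 9.4.1.1); event date equal to type 2 start (SAP 7.1.2); ET within 72 hours of that start (Protocol 7.9).

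**Step 1: reproduce Example 3.** Assumed days: rescue on Days 16-21 and 64-70, unscheduled visit on Day 63, ET on Day 88.
- Week 4: 29 - 21 = 8 days, under 28, so Week 2 is used.
- Week 8: 57 - 21 = 36 days, used as collected.
- Week 12: 85 - 70 = 15 days, so the Day 63 visit is used.
- Week 16 is missing for a related reason. ET is 88 - 70 = 18 days after rescue and ineligible, so Day 63 is used again.

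This matches the SAP. ET could not be a donor here before Day 70 + 28 = 98, so the example does not test the ET clause. It has no type 2 use either.

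**Step 2: apply the same rule to a type 2 case.** Hypothetical participant: type 2 starts on Day 70, ET on Day 73, then withdrawal.

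| Rescue history | ET minus end of rescue | Donor for Weeks 12 and 16, as written | Donor if post-type 2 values are barred |
|---|---|---|---|
| None | not applicable | ET, Day 73 | Week 8, Day 57 |
| Days 34-40 | 73 - 40 = 33 days | ET, Day 73 | Week 4, Day 29 |
| Days 54-60 | 73 - 60 = 13 days | Week 4, Day 29 | Week 4, Day 29 |

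In the second row Week 8 is itself only 57 - 40 = 17 days after rescue, so the next eligible value is Week 4. The ET score is carried forward in the first two rows and not in the third.

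**Step 3: set the texts against each other.** The EDPS1 opening limits the set to data before type 2 use. The donor clause adds ET to the pre-event period, so falling after the event does not exclude it. SAP 7.7 keeps ET out of analysis tables; following 7.7 instead gives the right-hand column in all three rows. Two programmers could build different datasets from the same SAP. Protocol 11.1.2 has no ET clause in its EDPS1, and SAP section 13 does not list the clause as a change.

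**Step 4: size, on assumptions only.** If every type 2 user had an eligible ET score after the start, the shrinkage in the difference in mean EASI percentage change at Week 16 would be

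shrinkage = (placebo share with type 2 use - active share) x gain at ET due to the new therapy.

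| Assumed shares, placebo vs active | Gain of 5 points | Gain of 30 points |
|---|---|---|
| 5% vs 2% | 0.03 x 5 = 0.15 | 0.03 x 30 = 0.9 |
| 10% vs 5% | 0.05 x 5 = 0.25 | 0.05 x 30 = 1.5 |
| 15% vs 5% | 0.10 x 5 = 0.5 | 0.10 x 30 = 3.0 |

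None of these shares or gains comes from the documents. The conditions in Step 2 reduce every entry, and earlier visits are affected less because later starters do not yet contribute.

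**The case against.** The strongest reply is that an ET score taken on type 2 treatment is itself data collected after type 2 use, so EDPS1 already bars it and SAP 7.7 confirms this. That is a reasonable reading of the intent, but it is not what the donor clause says. The clause names ET explicitly and tests it only against rescue and type 1 use. The conflict with 7.7 shows that the text needs reconciling; it does not settle which section prevails.

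Several other objections stand and limit the point:
- Protocol 6.9.1.2 describes systemic therapy or phototherapy as the step after topical rescue has failed. Recent rescue will often make ET ineligible, as in the third row of the Step 2 table. Neither Protocol 5.4 nor 6.9.2.3 requires prior rescue, however, so the gap is not closed.
- If the visit window is kept, exposure to the new therapy at ET is about three days at most. The wording does not strictly exclude a visit before the first dose. The SAP sets no limit if the visit is late.
- The value used instead may be weeks older and may predate the worsening that led to failure. The documents do not establish which donor is less biased overall.
- Under SAP 9.4.1.1 the strategy is applied to daily PP-NRS and SD-NRS scores, so the ET visit matters less for those two.

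A reader might infer that every type 2 user has an on-treatment score carried to Week 16, or that the whole trajectory after the event is wrong. The documents support neither: three conditions must hold together, and 7.7 points the other way.

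**Conclusion.** The point holds as a defect in the stated rule. Taken literally, SAP 7.1.2, 7.1.2.1, 9.4.1.1 and 9.5.1 allow an ET score collected on type 2 treatment to be carried to Week 16 when the participant left early, the ET visit took place, and it was at least 28 days after any rescue or type 1 use. This contradicts the opening of EDPS1 and SAP 7.7.

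The scope is limited. The primary endpoint and all responder endpoints are set to non-response and do not change. The exposure is in the visit-based continuous secondary and exploratory scores under EDPS1, and in the supportive EDPS2 analyses of EASI and vIGA*BSA.

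The size cannot be stated, because the documents give neither type 2 rates nor an effect of such therapy at ET. The 0.15 to 3.0 points in the working are illustrations under generous assumptions. A reader might take the protocol's remark on systemic corticosteroids as support for a large gain within 72 hours; it gives no size or time and does not cover the other type 2 therapies. The average effect is probably small. Its direction, shrinkage of the treatment difference, rests on the assumption that type 2 use is commoner on placebo.

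**What to change.** In SAP 7.1.2, 7.1.2.1, 9.4.1.1 and 9.5.1, add that a donor value must have been collected before the start of any type 2 medication. The ET visit then serves as a donor only if it precedes that start; otherwise the last eligible scheduled or rescue unscheduled visit before that date is used. State a convention for an ET visit on the same day as the type 2 start. EDPS2 follows by its cross-reference.

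Amend SAP 7.7 to say when ET data may be carried forward, so that it agrees with 7.1.2.1. Add a worked type 2 example, and list the ET clause in section 13 as a change from the protocol.

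The cost is one clause in four sections, an edit to 7.7 and a check of the imputation program. Medication and visit dates are already collected, and nothing in clinical conduct changes. The downside is that some participants will receive an older value that may predate their worsening. Listing the donor visit for each type 2 user would let readers judge this.

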7.1.2.2 Efficacy Data Point Set 2 (EDPS2)

EDPS2 consists of all data collected at a scheduled timepoint that is at least 28 days after use of TCS/TCI rescue therapy* or type 1 prohibited medication and before use of type 2 prohibited medication. Data collected less than 28 days after such use will be considered as missing and excluded from the analysis. Data missing due to withdrawal from the study for reasons considered related to study medication** and data after use of type 2 prohibited medication will be imputed as per EDPS1. Data missing for other reasons will not be replaced.

7.1.2.3 Efficacy Data Point Set 3 (EDPS3)

EDPS3 consists of EASI-50 responses collected at Week 16 that were evaluated at least 14 days after use of TCS/TCI rescue therapy* or type 1 prohibited medication and before use of type 2 prohibited medication. Data collected less than 14 days after such use or missing due to withdrawal from the study for reasons considered related to study medication** or data after use of type 2 prohibited medication will be imputed as non-response.

EASI-50 response missing for other reasons, including early withdrawal from the study due to reasons not considered related to study medication will not be replaced and will be considered as missing.

7.1.2.4 Efficacy Data Point Set 4 (EDPS4)

EDPS4 consists of EASI-50 responses collected at Week 16 that were evaluated at least 28 days after use of TCS/TCI rescue therapy* or type 1 prohibited medication and before use of type 2 prohibited medication. Data collected less than 28 days after such use will be replaced as per EDPS1. Data missing due to other reasons including early withdrawal from the study for any reason will not be replaced and be considered as missing. Data after use of type 2 prohibited medication will be considered missing.

7.1.2.5 Efficacy Data Point Set 5 (EDPS5)

EDPS5 is a subset of EDPS1 for the EASI-50 response data only, excluding any data collected or imputed after the unblinding of a participant or other protocol deviations affecting efficacy (whichever occurs first) and excluding all data from subjects who take <75% of expected doses ([Section 5.3.2.1](#)) or whose compliance with emollient use was <75% ([Section 5.3.2.2](#)).

7.1.2.6 Efficacy Data Point Set 6 (EDPS6)

EDPS6 consists of data collected in the absence of TCS/TCI rescue therapy* and type 1 prohibited medication at any time since Day 1 for the responder endpoints relating to EASI, vIGA and PP-NRS. Data collected after such use will be imputed as non-response. Data missing due to withdrawal from the study for reasons considered related to study medication** and data after use of type 2 prohibited medication will be imputed as per EDPS1.

Responses missing for other reasons, including early withdrawal from the study due to reasons not considered related to study medication will not be replaced and will be considered as missing.

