2. STUDY OBJECTIVE(S)

2.1. Primary Objectives

The study will compare four treatment regimens of EDP1815 with placebo in participants with atopic dermatitis who are using twice daily topical emollients.

The primary comparison of interest is the odds ratio for achievement of an EASI-50 response at Week 16. The primary trial objective is to show superiority of EDP1815 over placebo.

The primary comparison will be made using a treatment policy strategy with respect to study medication but without regard to treatment compliance or any changes in background therapy. A composite strategy will be used with respect to use of topical corticosteroid rescue therapy with any participants who use these less than 28 days prior to the Week 16 assessment being considered as non-responders. A composite strategy will also be used for participants who withdraw from the study prior to the Week 16 visit for reasons relating to study medication (e.g., related adverse event, lack of efficacy, requirement of for alternative therapy) also being considered as non-responders. A ‘while on treatment’ strategy will be used for participants who withdraw from the study prior to Week 16 for reasons considered unrelated to study medication, with the achievement of response at Week 16 being considered missing.

A number of supportive analyses to check the robustness of the primary estimand approach will be performed. These will consider

- Topical corticosteroid rescue therapy in the window of 2-4 weeks prior to study medication as having no effect and using the composite strategy only for use less than 14 days prior to the Week 16 visit
- Using a ‘while on treatment’ strategy for rescue medications with any Week 16 data collected less than 28 days after rescue medication use being considered missing.
- Using a ‘while on treatment’ strategy for discontinuation of the study for any reason before Week 16.
- Using a principal stratum strategy excluding participants who are non-compliant with respect to study medication or emollient use (<75% compliance), use a prohibited background therapy, take at least one dose of the incorrect study medication or who are unblinded prior to the end of the study.
- Using an alternative composite strategy for topical corticosteroid rescue therapy, with all participants who use any topical corticosteroid therapy at any time between Day 1 and Week 16 considered as non-responders at the Week 16 visit.

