EDPS5: Is a subset of DPS1 for the EASI-50 response data only, excluding any data collected or imputed after the use of a prohibited medication or the unblinding of a participant (whichever occurs first) and excluding all data from subjects who take <75% of expected doses or whose compliance with emollient use was <75% or did not complete the 12-week treatment period.

EDPS6: Consists of data collected in the absence of topical corticosteroid rescue therapy at any time since Day 1 for the responder endpoints relating to EASI, vIGA and PP-NRS. Data collected after such use or missing due to withdrawal from the study for reasons considered related to study medication will be imputed as non-response.

Responses missing for other reasons, including early withdrawal from the study due to reasons not considered related to study medication will not be replaced and will be considered as missing.

EDPS7: Contains all data collected as part of a count endpoint. A treatment policy strategy will be used for all intercurrent events other than discontinuation from the study which will use a while on treatment strategy (i.e., the collection period will be ended at the time of study discontinuation).

SDPS1: Consists of all observed data collected at a scheduled visit.

SDPS2: Consists of all observed data collected, including data from scheduled and unscheduled visits.

The FAS with EDPS1 are used to estimate the primary estimand and all secondary and exploratory estimands (excluding those relating to count endpoints).

The FAS with EDPS2-EDPS6 will be used to estimate supplementary estimands for the primary endpoint. The FAS with EDPS2 and EDPS6 will be used to estimate supplementary estimands for selected secondary estimands.

The FAS with EDPS7 are used to estimate the secondary estimands relating to count endpoints.

The SAS and SDPS1 are used to present safety data assigned to specific scheduled visits.

The SAS and SDPS2 are used to present all other safety data, including adverse events.

Note that all subjects who withdraw from the study prematurely will be evaluated prior to database lock and unblinding will have their reason for withdrawal evaluated as being related or non-related to study medication.

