²Prohibited concomitant medications which may affect efficacy requiring IMP discontinuation. Such medications use will be recorded as protocol deviation. Classification will be provided by the sponsor in a separate spreadsheet.

If multiple events occurred, composite and while-on-treatment strategies are prioritized over treatment policy strategy. If multiple events requiring composite and while-on-treatment strategies occurred, study discontinuation due to treatment related reason and type 2 prohibited medication

strategy will be prioritized. If data does not change after applying composite strategy (for example, there is a treatment discontinuation due to related reason event and scheduled visit after treatment discontinuation was performed and so data from this visit will not be replaced), other events strategies still may be applied.

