Supplementary Estimand 3	EDPS4	
If <28 days before Week 16 visit: Composite strategy (as per primary estimand)
 
If ≥28 days before Week 16 visit: Treatment policy strategy (as per primary estimand)
	
If type 2 prohibited medication² used: While-on-treatment Strategy Data will be considered missing from the date of medication start
 
If study discontinuation: While-on-treatment strategy Data will be considered missing from the date of treatment discontinuation
	Treatment policy strategy (as per primary estimand)

Estimand	EDPS	Intercurrent event		
		Use* of Permitted TCS/TCI Rescue Therapy or Type 1 Prohibited Medications ¹	Study Discontinuation Before Week 16 Visit or Type 2 Prohibited Medications ² Use ³	Noncompliance or Unblinding or Other Protocol Deviations Affecting Efficacy Before Week 16
Supplementary Estimand 4	EDPS5	As per primary estimand unless data is already excluded due to non-compliance or unblinding or other protocol deviations affecting efficacy	As per primary estimand unless data is already excluded due to non-compliance or unblinding or other protocol deviations affecting efficacy	While-on-treatment strategy Data collected after the intercurrent event will be excluded
Supplementary Estimand 5	EDPS6	Composite strategy Participants with use at any time between Day 1 and the Week 16 visit will be considered as non-responders at all visits after the relevant medication was used.	If type 2 prohibited medication² used: Composite strategy (as per primary estimand) If due to related** reason: Composite strategy (as per primary estimand) If due to non-related** reason: While-on-treatment strategy (as per primary estimand)	Treatment policy strategy (as per primary estimand)

* Consider the last day with therapy for participant before Week 16.

** Treatment discontinuation reasons will be checked. Reasons related to study medication are lack of efficacy, treatment failure, adverse event (if related). Also, withdrawal of consent may be considered related to study medication based on the clarification text provided, that will be assessed by the Evelo team and provided in a separate spreadsheet. Non-related reasons are all other reasons.

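### EDPS6 leaves a rescued participant who later withdraws for a non-related reason as missing at Week 16, although the rescue rule of Supplementary Estimand 5 already fixes that participant as a non-responder, and no rule ranks the two

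*SAP*

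**What the plan says.** **The estimand, rescue side.** Protocol 2.1 describes the alternative composite strategy "with all participants who use any topical corticosteroid therapy at any time between Day 1 and Week 16 considered as non-responders" at Week 16. Protocol Table 11-1 repeats this for Supplementary Estimand 5. Protocol 11.3.2 extends it to all timepoints after rescue for the EASI, vIGA and PP-NRS responder endpoints. The rescue column of SAP Table 2 (9.3.2) reads "Participants with use at any time between Day 1 and the Week 16 visit will be considered as non-responders at all visits" after the medication was used. The SAP widens the event from topical corticosteroids to TCS/TCI rescue and type 1 prohibited medication. None of these texts is limited to visits that took place.

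**The estimand, discontinuation side.** The same row of SAP Table 2 says "If due to non-related reason: While-on-treatment strategy", as for the primary estimand, where missing data are not replaced.

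**The data set.** SAP 7.1.2.6 says "Data collected after such use will be imputed as non-response". Withdrawal for related reasons and data after type 2 medication are handled as in EDPS1. For the rest, "Responses missing for other reasons, including early withdrawal from the study due to reasons not considered related to study medication will not be replaced". Protocol 11.1.2 has the same structure: it imputes non-response for "Data collected after such use or missing due to withdrawal from the study for reasons considered related to study medication" and leaves other missing responses as missing.

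**The priority rule.** SAP 9.3.1 says "If multiple events requiring composite and while-on-treatment strategies occurred, study discontinuation due to treatment related reason" and type 2 medication take priority. It does not mention rescue combined with non-related withdrawal.

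**Use.** The logistic model takes Week 16 data only (SAP 9.3.3). SAP 15.2.1 flags four EDPS6 tables for top-level results: the EASI-50 summary (14.2.1.1.6), logistic regression (14.2.1.2.6) and GLMM (14.2.1.3.3), and the EASI-75 GLMM (14.2.2.3).

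**The concern.** Take a participant rescued in Week 3 who stays on study treatment, as Protocol 6.9.1.2 provides, and moves away in Week 10. Under the primary estimand this early rescue does not determine the Week 16 outcome, so leaving Week 16 missing is coherent. Under Supplementary Estimand 5 the Week 3 rescue settles every later visit. EDPS6 nevertheless imputes only collected data, so Week 16 is missing and the participant drops out of the Week 16 model. The same happens after type 1 medication, or when a rescued participant misses Week 16 for another non-related reason.

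Two programmers could code this participant differently, each with SAP text in support. The coding also depends on how the withdrawal reason is classified. For withdrawn consent, the sponsor's team makes that judgement from clarification text (SAP 7.1.2). If the rescue rule were applied in full, a rescued participant's status would not depend on it.

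**Working it through.** **1. The plan's own figures.** With 25% vs 50% response, two-sided 5% and 80% power (SAP Section 6), the pooled-variance formula without continuity correction gives 58 per group (power 80.2%), and 58/(1 − 0.20) = 72.5, so 73. Both match the SAP. They are not in question; they supply the planning rates and the 20% drop-out used below.

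**2. The texts side by side, for rescue followed by non-related withdrawal, at Week 16.**

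| Text | Week 16 status |
|---|---|
| Protocol 2.1, Table 11-1, 11.3.2 | Non-responder |
| SAP Table 2, rescue column | Non-responder |
| SAP Table 2, discontinuation column | Missing |
| SAP 7.1.2.6 and Protocol 11.1.2 (EDPS6) | Missing |
| SAP 9.3.1 priority rule | Not addressed |

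**3. Effect under assumed rates.** Let q be the proportion ever rescued, r the response rate if never rescued, and w1 and w0 the non-related withdrawal rates with and without rescue. The documents give none of these; all values are assumptions.

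- Rescue rule applied in full: (1−q)(1−w0)r / [q + (1−q)(1−w0)]
- EDPS6 as written: (1−q)(1−w0)r / [q(1−w1) + (1−q)(1−w0)]

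Never-rescued withdrawals are missing in both formulas, so the difference comes only from the rescued ones. Throughout, w0 = 0.10, with r = 0.35 on placebo and 0.60 on active.

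Placebo, q = 0.40, w1 = 0.30: 0.189/0.94 = 20.1% in full; 0.189/0.82 = 23.0% as written.
Active, q = 0.20, w1 = 0.30: 0.432/0.92 = 47.0% in full; 0.432/0.86 = 50.2% as written.
Odds ratio: (0.432/0.488)/(0.189/0.751) = 3.52 in full; (0.432/0.428)/(0.189/0.631) = 3.37 as written.

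| q placebo / active | w1 | Placebo, full → written | Active, full → written | OR, full → written |
|---|---|---|---|---|
| 0.40 / 0.20 | 0.30 | 20.1% → 23.0% | 47.0% → 50.2% | 3.52 → 3.37 |
| 0.30 / 0.30 | 0.30 | 23.7% → 26.3% | 40.6% → 45.0% | 2.20 → 2.30 |
| 0.40 / 0.20 | 0.10 | 20.1% → 21.0% | 47.0% → 48.0% | 3.52 → 3.47 |
| 0.30 / 0.30 | 0.10 | 23.7% → 24.5% | 40.6% → 42.0% | 2.20 → 2.23 |

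In the first row the rescued participants left out number 75 × 0.40 × 0.30 = 9 on placebo and 75 × 0.20 × 0.30 = 4.5 on active.

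**4. Cross-check with counts.** Assume 75 per arm, 15 drop-outs and 60 evaluable, with 15/60 and 30/60 responders (crude odds ratio 3.00). Recode k missing rescued participants per arm as non-responders: OR = [30/(30 + k active)] / [15/(45 + k placebo)].

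| k placebo / active | Placebo | Active | OR |
|---|---|---|---|
| 3 / 3 | 23.8% | 47.6% | 2.91 |
| 6 / 6 | 22.7% | 45.5% | 2.83 |
| 15 / 15 (every drop-out) | 20.0% | 40.0% | 2.67 |
| 6 / 0 | 22.7% | 50.0% | 3.40 |
| 0 / 6 | 25.0% | 45.5% | 2.50 |

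Recoding lowers the rate in each affected arm. The direction for the odds ratio depends on the split between arms.

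**The case against.** The strongest defence is that EDPS6 faithfully implements the discontinuation column of its own Table 2 row. That stands, and it rules out a tempting stronger reading: a reader might infer that EDPS6 contradicts a settled estimand. The conflict lies inside the estimand row, and the SAP never says which column wins. Protocol 2.1 and 11.3.2 favour the rescue rule, and calling the as-written rates too high rests on that reading.

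Three further inferences go beyond the documents or the arithmetic:

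- *The rule drops only certain non-responders.* It also leaves never-rescued non-related withdrawals missing. Only the previously rescued subset has a fixed outcome.
- *The arm with more rescue followed by withdrawal is inflated more.* In the first row of the step 3 table, placebo loses 9 and rises 2.9 points, while active loses 4.5 and rises 3.3.
- *The GLMM is affected to the same degree.* It uses all visits (SAP 9.4.2.2), so attended post-rescue visits stay in as non-responses and inform the missing Week 16 value. That effect was not computed and may be smaller.

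The size is also open to challenge. The larger shifts assume non-related withdrawal three times as frequent after rescue. The withdrawals most plausibly tied to rescue (lack of efficacy, treatment failure, related adverse events) already count as related and become non-responses. The first row implies non-related withdrawal of 0.40 × 0.30 + 0.60 × 0.10 = 18% on placebo and 0.20 × 0.30 + 0.80 × 0.10 = 14% on active, most of the planned 20% drop-out. Even then the odds ratio moves by only about 4%.

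**Conclusion.** The point holds. As written, EDPS6 leaves missing some participants whose Week 16 outcome the rescue rule of its estimand has already fixed, and nothing in either document resolves the overlap. Taking the rescue rule as the intended one, the crude and logistic Week 16 EASI-50 rates are overstated in any arm with such participants. Under the assumed rates this is about 1 point per arm with 10% non-related withdrawal throughout, and 2.5 to 4.4 points with 30% after rescue. The odds ratio can move in either direction, so the documents do not support a claim that the rule favours EDP1815.

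The primary analysis uses EDPS1 and is outside this point. EDPS6 is supplementary, and the SAP is uneven about it: Section 8 lists EDPS2 to EDPS5 for the primary endpoint and 9.3.3 speaks of four supplementary estimands, while 9.3.2 counts five. Its EASI-50 and EASI-75 tables are nevertheless flagged for top-level results, which is reason enough to settle the coding. The EDPS6 tables for EASI-90, vIGA and PP-NRS follow the same rule but carry no such flag.

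**What to change.** - In SAP 7.1.2.6, state that from the first TCS/TCI rescue or type 1 medication on or after Day 1, every later scheduled visit through Week 16 is a non-response, whether or not the visit was performed and whatever the reason for any later withdrawal. The words on or after keep Day 1 use inside the rule, as 7.1.2.6 and Table 2 require.
- In SAP 9.3.1 and the Supplementary Estimand 5 row of Table 2, state that for EDPS6 the rescue/type 1 composite takes precedence over non-related withdrawal.
- List this in SAP Section 13 as a change from Protocol 11.1.2, whose EDPS6 text has the same gap.

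The cost is a few sentences and one derivation flag, with no new data. Reported EDPS6 response rates would be slightly lower. Never-rescued participants who withdraw for non-related reasons stay missing as now.
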